9.7 Data analysis

All data analyses will be performed using SAS statistical software version 9.4., and will be reported in a manner consistent with the Strengthening the Reporting of Observational Studies in Epidemiology (STROBE) guidelines.

Descriptive statistics will be used to present the data where continuous variables will be summarized as mean, standard deviation, median, minimum and maximum. Categorical variables will be described by frequencies and related percentages. Summaries will be reported separately for the elderly +75 years (cohort 1 and 2) and patients with renal impairment (cohort 2). Annual frequency of different OAC treatment during the study period in addition to adherence to each NOACs (high, moderate, low, and poor) will be presented. Also a separate analysis will be done to characterize patients with NVAf who have not been treated with OAC.

In the following, cohort 1 (registry) and cohort 2 (EMR) will be analyzed separately, but using the same analytical approaches.

The analyses will be performed on the total sample as well as on a confounder adjusted sample. It has to be kept in mind that analyses based on the overall sample (non-confounder adjusted sample) is prone to bias (see section 9.9).

Three separate propensity score models will be conducted and a 1:1 matching will be performed for:

- warfarin vs apixaban
- warfarin vs dabigatran
- warfarin vs rivaroxaban.

No matching to compare the NOACs among each other (e.g. apixaban vs rivaroxaban) will be performed due to underlying differences in prescribing preferences of different NOACs.

The propensity scores (PS) will be based on demographic variables and clinically relevant medical history, e.g. cardiovascular risk factors, comorbidities and concomitant medications at baseline.

Patients who switch or discontinue the OAC treatment will be censored at the date of switch or discontinuation. It cannot be ruled out that the switch of OAC (censoring) could be informative, but it is handled as uninformative censoring in the analyses.

Detailed methodology for propensity score modeling, matching, handling of missing data, summary and statistical analyses in this study will be documented in a Statistical Analysis Plan (SAP), which will be dated, filed and maintained by the sponsor. The SAP may modify the plans outlined in the protocol; any major modifications of primary endpoint definitions or their analyses would be reflected in a protocol amendment.

9.7.1 Analysis of primary outcome(s)

The incidence rates and corresponding 95% confidence intervals for ischemic stroke and intracranial hemorrhage will be calculated for warfarin, apixaban, dabigatran and rivaroxaban cohorts on a confounder adjusted population.

The person time at risk will be calculated from first OAC use during the study period until a certain outcome, death or end of follow-up in June 30, 2018 (or later depending on the availability of data). The incidence rates will be calculated by the number of first cases of a certain event during the follow-up divided by person time at risk and will be presented per 100 (or 1000) patient years with exact 95% Confidence Interval (Poisson distribution) for all outcomes of interest, and separately for each OAC.

To compare outcomes of interest in cohorts of warfarin with apixaban, dabigatran and rivaroxaban users, the incidence rate ratios and corresponding 95% confidence intervals will be calculated.

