The duration of dispensation (DoD) will be set as the date of a dispensed prescription plus the estimated duration of that prescription (duration of OAC supply estimated from the dispensed pack-size and strength).

The following rules applies:

1. If the next dispensed prescription was for the same OAC within 30 days after end of DoD there was a continuous treatment
2. If a new dispensed prescription for another OAC occurred within DoD or within 30 days after end of DoD there was a switch in OACs (switching date = date of dispensation)
3. If the next dispensed prescription was for the same OAC more than 30 days after end DoD there was a discontinuation (discontinuation date = date of DoD + 30 days)

A 30-day gap period is included to take into account incomplete adherence to treatment. The figure underneath displays the three different scenarios. In sensitivity analyses the gap period will be varied from 30 days to 0 days, 15 days and 60 days, respectively.

[figure not shown]

Figure 4: Definition of continuation, switch and discontinuation

Patients to be included in the effectiveness and safety analysis should have a supply of OAC covering the event, plus a 30 days grace period for those patients discontinuing their therapy. Any event happening after the date of discontinuation plus 30 days or after a switch in OAC therapy will not be included.

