9.3.3 Estimation of OAC adherence

Proportion of days covered (PDC) will be estimated for each individual from the index medication date and onwards. The PDC is defined as the number of days that the index medication was on hand during the time period divided by the total number of days in the period. For instance if the length of the time period is 100 days and the NOAC supply covers 50 days, the adherence is estimated to 50%.

Likewise, the age- and sex-specific median doses of warfarin (using the two methods described in 9.3.2) will be used to calculate to warfarin supply.

If the OAC supply last longer than the study period the adherence is set to 100%. The proportion of days covered (PDC) will take into account the patient's entire follow-up period, defining end of study period as death, end of study, migration, discontinuation or switch of OAC therapy. In addition to the entire period, adherence will also be estimated at fixed time intervals after OAC index date, i.e. 3 months (90 days), 6 months (180 days), and 9 months (270 days), 1 year (365 days), 2 years (730 days) and 3 years (1095 days).

Consecutive dispensations of the same OAC will be combined and corrected for overlap. For treatment gaps equal or less than 30 days of the previous OAC dispensation it is assumed the patient is on continuous therapy. The length of the gap period will be varied in sensitivity analyses down to 0 and 15 days and up to 60 days.

Some patients switch to another NOAC during follow-up and the day of switch will be defined as the end of the time period. Separately, the PDC for use of any OAC during the study period will be estimated, which accounts for therapy switching during follow-up.

PDC will be estimated as the mean PDC for each OAC as well as grouped into four categories of high adherence (≥ 0.80), moderate adherence (0.50-0.79), low adherence (0.20-0.49) and poor adherence (<0.20). Adherence will also be reported as dichotomized using the conventional PDC of <0.80 or ≥ 0.80 as cutoff. Percentage point differences between OAC user groups will be presented. Analyses of OAC adherence will account for differences in follow-up time and baseline characteristics, such as standard and reduced dosing level.

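### The protocol gives three conflicting end-of-risk rules for the primary incidence rates, and the event window in 9.3.2 matches neither person-time rule

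*Protocol*

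**What the plan says.** Three ends of the risk period can be read from the Protocol for the same primary rates.

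1. **End of data.** Section 9.7.1 (Analysis of primary outcome(s)): "The person time at risk will be calculated from first OAC use during the study period until a certain outcome, death or end of follow-up", given as 30 June 2018 or later. Its numerator is tied to the same period: "The incidence rates will be calculated by the number of first cases of a certain event during the follow-up divided by person time at risk". The population paragraph of the abstract likewise gives only outcome, end of study and death.
2. **End of supply plus 30 days, or switch.** Section 9.7 (Data analysis), the parent of 9.7.1: "Patients who switch or discontinue the OAC treatment will be censored at the date of switch or discontinuation". Sections 9.2 (Setting) and 9.2.1 (Study time frame) say the same. Section 9.3.2 (OAC exposure) fixes the date: "discontinuation date = date of DoD + 30 days", where DoD is the duration of dispensation, that is, the estimated supply.
3. **End of supply plus 60 days, or switch, for events.** Section 9.3.2: "Any event happening after the date of discontinuation plus 30 days or after a switch in OAC therapy will not be included". The sentence just before describes a single allowance: patients "should have a supply of OAC covering the event, plus a 30 days grace period for those patients discontinuing their therapy".

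Emigration appears in none of these rules. Section 9.3.3 does use migration, but for adherence, "defining end of study period as death, end of study, migration, discontinuation or switch of OAC therapy", and Table 4 marks censoring as the use of the adjoining migration-date rows.

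**The concern.** An incidence rate means something only if every counted event could have occurred in the counted person-time, and the reverse. The 9.3.2 event window ends earlier than the 9.7.1 person-time and later than the 9.7 person-time, so it fits neither.

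The rates and their ratios against warfarin are the primary result for both ischemic stroke and intracranial hemorrhage. A mismatch that depends on how long patients stay on treatment cancels in the ratio only if persistence is the same in both arms. Even the measurement of persistence differs: 9.3.2 takes NOAC supply from fixed daily dosing but estimates warfarin supply from a median daily dose by age group and sex. Two programmers working from different sections could therefore produce different primary rates, each with support in the text.

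**Working it through.** **Figures in the plan.** No stated figure depends on the person-time rule. Tables 7–10 in 9.5 rest on proportions and matched numbers, which reproduce: 70,000 × 0.11 × 0.90 = 6,930; 70,000 × 0.17 × 0.90 = 10,710; 70,000 × 0.19 × 0.90 = 11,970. The Clopper-Pearson limits in Tables 7 and 9 also reproduce, and the relative-risk limits in Tables 8 and 10 agree to within 0.01. They are unaffected by this point.

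**Reference rates.** From 9.5, the warfarin risks are 2.43% and 1.23% over a mean of 18 months. If those 18 months are time at risk, the rates are 2.43/1.5 = 1.62 and 1.23/1.5 = 0.82 per 100 patient-years.

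**The rules combined**

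| Person-time ends | Events end | Result |
|---|---|---|
| End of data (9.7.1) | End of data (9.7.1 read alone) | Consistent, but counts time and events off treatment, against 9.7 and 9.3.2 |
| Supply + 30 (9.7) | Supply + 30 | Consistent |
| Supply + 30 (9.7) | Supply + 60 (9.3.2) | Events without person-time; rates too high |
| End of data (9.7.1) | Supply + 60 (9.3.2) | Person-time without events; rates too low |

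**Size of the two mismatches.** Assumptions, none of them from the Protocol except the calendar dates:
- entry uniform over 1 January 2014 to 31 May 2018 with data to 30 June 2018, so available follow-up A is uniform on 1 to 54 months, mean (1 + 54)/2 = 27.5;
- end of supply D exponential with monthly rate h = −ln(1 − p)/12, where p is the assumed share discontinuing by 12 months;
- constant event hazard; deaths, outcomes and switches ignored;
- c = 30 days = 0.986 month.

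Mean time in each window is E[min(D + c, A)] for supply + 30, E[min(D + 2c, A)] for supply + 60, and E[A] for end of data. Under a constant hazard, calculated rate / true rate = mean event window / mean person-time.

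| p | Supply + 30 (months) | Supply + 60 (months) | Supply + 60 over supply + 30 | Supply + 60 over 27.5 |
|---|---|---|---|---|
| 10% | 23.83 | 24.02 | 1.008 | 0.873 |
| 20% | 20.58 | 20.94 | 1.017 | 0.761 |
| 30% | 17.69 | 18.17 | 1.027 | 0.661 |
| 40% | 15.16 | 15.75 | 1.039 | 0.573 |
| 50% | 12.91 | 13.58 | 1.052 | 0.494 |

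- *9.7 person-time with 9.3.2 events:* rates too high by about 1% to 5%. Even with 10% discontinuing in one arm and 50% in the other, the ratio is off by only 1.052/1.008 = 1.04.
- *Literal 9.7.1 person-time with 9.3.2 events:* rates too low by about 13% to 51%. The ischemic stroke rate of 1.62 would be reported as 1.62 × 0.873 = 1.41 down to 1.62 × 0.494 = 0.80 per 100 patient-years.

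**Effect on the ratio in the second case.** With a true ratio of 1.00, the reported ratio is the NOAC event-window share divided by the warfarin share. For assumed shares of 0.8 and 0.7 it is 0.8/0.7 = 1.14; with the shares reversed it is 0.7/0.8 = 0.875.

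**The case against.** The best defense is that 9.7.1 is shorthand. Its parent section has just stated the censoring and discussed whether it is informative. Section 9.2 lists the same criteria. Section 9.2.1, speaking of the main analysis, first names only endpoint, end of study and death and then adds censoring at switch or discontinuation in the next sentence, so the authors do write this way. Read alone, 9.7.1 is also internally consistent, since its numerator and denominator share one follow-up period.

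This stands, and it disposes of a stronger reading. A reader might infer from 9.7.1 that the primary denominator is settled as running to June 2018 whatever the treatment, and that the rates are therefore heavily diluted. The Protocol does not support that: three sections state on-treatment censoring. A reader might also set 27.5 months of potential follow-up against the stated mean of 18 and conclude that the denominator is 27.5/18 = 1.5 times too large. That requires the 18 months to be on-treatment time, which the Protocol does not say, and entry to be uniform with no deaths.

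On the second 30 days, the authors may have used discontinuation loosely to mean end of supply, and a standard program that censors at supply + 30 would not count later events. That is plausible, but 9.3.2 defines the discontinuation date explicitly a few lines earlier, so the literal text still gives supply + 60. The analysis plan, not seen here, may settle the matter; that would not remove the contradiction from the Protocol.

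**Conclusion.** The point holds as a contradiction in the text that governs both primary rates. Three end-of-risk rules are stated, and the 9.3.2 event window agrees with neither person-time rule.

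On the more natural reading, with 9.7.1 inheriting the censoring, the numerical harm is small: about 1–5% on the rates and little on the ratio. A raised event rate just after stopping would enlarge it. On the literal reading combined with the 9.3.2 event rule, the harm is large, about 13–51% on the rates, with a ratio biased in a direction that cannot be known beforehand. All sizes rest on assumed discontinuation of 10–50% at 12 months and a constant hazard; the Protocol reports no persistence data and none by drug. They show why the wording matters and do not predict the study's bias.

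**What to change.** State one at-risk window in 9.7.1 and use it for events and person-time alike: from the index date to the earliest of first outcome, switch, discontinuation date as already defined in 9.3.2 (end of supply plus 30 days, one grace period), emigration, death, or end of data. In 9.3.2, delete the second addition of 30 days in the sentence on excluded events, so that it agrees with the sentence before it. Align the lists in the abstract, 9.2 and 9.2.1, including emigration.

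If follow-up regardless of treatment is also wanted, run it as a labelled sensitivity analysis that counts all events and all time to the end of data.

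The cost is a wording change to the Protocol, a matching line in the analysis plan, and programming. No new data are needed. Because the change settles how the primary outcomes are analyzed, it should be made before the primary analysis is run.

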9.7.2 Further Analyses

The incidence rates and corresponding 95% confidence intervals for overall stroke (ischemic, hemorrhagic, other unspecified) and systemic embolism outcomes, myocardial infarction, all-cause mortality and major bleeding as defined by ISTH and the Cunningham algorithm (in a sub-set of patients; cohort 2) will be calculated for warfarin, apixaban, dabigatran and rivaroxaban cohorts.

Patients will be characterized according to demographic variables (age, gender), relevant medical history within 5 years prior to index date, different comorbidity risk scores (modified HAS-BLED, CHA2DS2VASC score, Charlson co-morbidity index), trends in OAC utilization from time of reimbursement, concomitant medications by OAC use and for NOACs-users, by the dose (standard or reduced) at start of follow up. Tests for differences between OAC sub-groups will be conducted using t-test, chi-square tests; the generalized linear model will be obtained to adjust for age and gender.

Additional analyses like a Cox proportional hazards regression models will be used to compare event rates of interest between the cohorts of users of different NOACs and warfarin adjusted for baseline covariates including age, gender, relevant medical history and concomitant medications. Hazard ratios with 95% confidence intervals for each study outcome will be presented (tables and Forest plots).

The occurrence of the first primary outcomes, as well as for the secondary outcomes among NVAF patients in warfarin versus NOACs will be described by Kaplan-Meier curves. The cumulative incidence of bleeding will be presented within different time windows (3m, 6m, 9m, 1 year, 2 years up until end of the follow-up).

Further details about the analysis and sensitivity analysis like Cox models evaluated within quintiles of PS probabilities can be found in the SAP.

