8.2 Secondary objectives

- To assess the incidence rates of:

- overall stroke (ischemic, hemorrhagic, other unspecified) and systemic embolism outcomes;
- myocardial infarction;
- all-cause mortality;
- major bleeding as defined by ISTH and the Cunningham algorithm (in a sub-set of patients; cohort 2)

in OAC naïve NVAF patients who are dispensed individual NOACs for the first time and compare with the corresponding rates in OAC naïve users of warfarin in the overall and in a propensity score matched population.

- To describe and compare demographic and clinical characteristics (age, gender, CHA₂DS₂-VASc and HAS-BLED score, bleeding history, concomitant medications and co-morbidities) as well as drug utilization patterns of NVAF patients who initiated an OAC (NOACs and warfarin) in the study period.

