9.5 Study size

There is no underlying hypothesis to confirm or reject. The sample is determined by eligibility. However it is desirable to assess the suitability of the available sample to produce useful estimates of the main outcomes.

The ratio of dispensations between the different NOACs and warfarin is estimated based on average number of dispensations in the period of 2014-2016 as given by NorPD statistics. Approximately half of patients treated with OAC have a dispensation for warfarin, 17%, 19% and 11% for apixaban, rivaroxaban and dabigatran respectively (Table 6). Based on previous studies, we estimate the risk of ischemic stroke and intracranial hemorrhage in the warfarin group, during an assumed mean follow-up of 18 months, to be 2.43% and 1.23% respectively.(1-4, 13-15)

ATC code and drug	2013	2014	2015	2016
	B01AA03- warfarin	87,994	77,755	69,289
B01AF02 – apixaban	2,260	8,640	21,507	37,276
B01AF01 – rivaroxaban	13,423	20,795	25,480	28,924
B01AE07 - dabigatran	13,879	15,358	13,843	13,327
Total	117,556	122,548	130,119	139,884

Table 6: Number of patients with at least one dispensation of an OAC annually in the period 2013 to 2016 as given by NorPD. The table gives the total OAC use for all indications.

The study population will comprise all adult OAC naïve NVAF patients in Norway who filled a prescription for an OAC (rivaroxaban, apixaban, dabigatran, warfarin) in the study period, defined as from 1 January 2014 to 30 June 2018 (or later depending on availability of data). Based on Table 6 demonstrating the total number of new prescriptions for OACs in 2013-2016 and based on a publication describing Norwegian NVAF patients, the sample size of naïve patients available for the study will be approximately 70,000 patients; however, as known from previous unpublished data, the proportion of naïve patients who get prescribed a NOACs is likely to be increasing in the last several years.

The tables below show the precision for the proportions and relative risks of ischemic stroke and intracranial hemorrhage that might be expected in terms of width of 95% confidence intervals.

Assuming that 90% of dabigatran, apixaban or rivaroxaban patients can be propensity score matched with patients treated with warfarin, the 95% confidence intervals for the matched proportions show a sufficient precision for ischemic stroke and intracranial hemorrhage (see tables below).

1:1 propensity score matched with warfarin			

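### Comparing baseline characteristics by t-tests and chi-square tests in about 70,000 patients will not show which differences between anticoagulants are relevant; standardized differences should be the basis

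*Protocol*

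**What the plan says.** Protocol section 8.2 sets as a secondary objective: "To describe and compare demographic and clinical characteristics" of patients who start an OAC. The method is in section 9.7.2: "Tests for differences between OAC sub-groups will be conducted using t-test, chi-square tests". The same sentence continues that "the generalized linear model will be obtained to adjust for age and gender".

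Section 9.7 also plans ordinary descriptive summaries (mean, standard deviation, median and range, or frequencies and percentages). It adds: "The analyses will be performed on the total sample as well as on a confounder adjusted sample". Detail on propensity score modelling, matching and statistical analysis is left to the SAP.

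On size, section 9.5 opens with "There is no underlying hypothesis to confirm or reject". It expects that the number of naïve patients "available for the study will be approximately 70,000 patients" and gives the split: "Approximately half of patients treated with OAC have a dispensation for warfarin, 17%, 19% and 11% for apixaban, rivaroxaban and dabigatran respectively".

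The protocol gives no significance level for these tests, no standardized difference and no limit above which a difference between groups counts as relevant.

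**The concern.** A t-test or chi-square test asks whether a difference is distinguishable from zero. In groups of this size almost any real difference is, so the p-value mainly reports how many patients there were. The question behind the objective is a different one: how far do the patients given each drug differ, and in which respects? Section 9.9 names channeling as a potential limitation, and the characteristics tables are where a reader would judge its extent. If most rows are significant, the p-values do not separate an imbalance that bears on interpretation from one that does not.

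The protocol does not leave this choice open. It names the tests as the tool for comparing groups, in a study whose primary analysis (section 9.7.1) is otherwise one of estimation with confidence intervals.

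**Working it through.** **Inputs.** From section 9.5: 70,000 patients; 17% apixaban, 19% rivaroxaban, 11% dabigatran. The remainder is 100 − 17 − 19 − 11 = 53% warfarin, in line with the protocol's *approximately half*. Assumptions not in the protocol: two-sided α = 0.05, an illustrative comorbidity prevalence of 20%, and 0.1 as the conventional limit for a negligible standardized difference.

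**Step 1: reproduce the plan's own figures.** Section 9.5 states: "Assuming that 90% of dabigatran, apixaban or rivaroxaban patients can be propensity score matched with patients treated with warfarin". Then:
- dabigatran 70,000 × 0.11 × 0.90 = 6,930
- apixaban 70,000 × 0.17 × 0.90 = 10,710
- rivaroxaban 70,000 × 0.19 × 0.90 = 11,970

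These are the group sizes in Tables 7 to 10. Before matching, the groups are 7,700, 11,900 and 13,300, against 70,000 × 0.53 = 37,100 on warfarin.

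**Step 2: smallest standardized difference that reaches p < 0.05.** The standard error is SE = √(1/n₁ + 1/n₂) and the threshold is 1.96 × SE. For prevalence p, the threshold in percentage points is 100 × 1.96 × SE × √(p(1 − p)); at p = 0.20 the root is 0.40.

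| Warfarin (37,100) versus | SE | Threshold | At 20% prevalence |
|---|---|---|---|
| dabigatran (7,700) | 0.01252 | 0.0245 | 0.98 points |
| apixaban (11,900) | 0.01054 | 0.0206 | 0.83 points |
| rivaroxaban (13,300) | 0.01011 | 0.0198 | 0.79 points |

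The significance line is thus four to five times below the conventional 0.1.

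**Step 3: probability of flagging a standardized difference of 0.05** (half the conventional limit), Φ(0.05/SE − 1.96):
- dabigatran Φ(3.99 − 1.96) = 0.979
- apixaban Φ(4.75 − 1.96) = 0.997
- rivaroxaban Φ(4.95 − 1.96) = 0.999

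**Step 4: would a multiplicity correction help?** The protocol does not state a number of tests. Suppose 150 (about 50 variables in Table 4 times three contrasts with warfarin). Bonferroni gives α = 0.05/150 = 0.00033, with critical value 3.588. The probability of flagging 0.05 is then Φ(0.05/SE − 3.588) = 0.66, 0.88 and 0.91. The correction moves the line to standardized differences of 0.036 to 0.045, still less than half the conventional limit.

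**Step 5: sensitivity.**
- With 35,000 on warfarin (exactly half), the thresholds are 0.0247, 0.0208 and 0.0200.
- If only 35,000 patients in all were eligible, every threshold rises by √2, to 0.035, 0.029 and 0.028.
- In the matched sets, 1.96 × √(2/n) gives 0.033, 0.027 and 0.025.

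The conclusion is the same in each case.

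**The case against.** The strongest reply is that the tests do not stand alone. Group means, standard deviations and percentages are planned, so the size of each difference will be visible beside any p-value, and a standardized difference can be computed from those summaries. The 9.7.2 sentence also includes a model for age and gender. No rule in the protocol turns a p-value into a conclusion, and the SAP may add more. All of this is correct and limits the point. It does not remove it, because the only comparison tool named is the significance test. P-values from the generalized linear model depend on sample size in the same way.

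Four stronger readings are tempting, and the protocol does not support them:
- *The comparisons are unadjusted.* This is true of the t-tests and chi-square tests themselves, but the same sentence adds the age- and gender-adjusted model.
- *About 150 tests will yield a known number of false positives.* The count is a reconstruction from Table 4. A false-positive count would also assume no true differences, whereas section 9.9 expects treatment choice to depend on baseline characteristics. Sample size is the driver, not the number of tests.
- *Balance after matching will be judged by these tests.* Section 9.7 runs analyses on both samples, but nothing says how balance is assessed, and matching detail is left to the SAP.
- *The tests breach the statement that there is no hypothesis.* That sentence explains why the sample is set by eligibility. It does not forbid descriptive p-values.

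**Conclusion.** The point holds as a limited one. The method named in section 9.7.2 is poorly suited to its objective at this sample size: significance is reached at standardized differences of about 0.020 to 0.025, and a difference of 0.05 is flagged with probability of about 98% or more. This rests on the planning figures of section 9.5, a conventional two-sided 0.05 level and simple two-group comparisons with warfarin. Halving the total sample leaves the thresholds at 0.028 to 0.035, so the result is not sensitive to those figures.

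The consequence is confined to a secondary, descriptive objective. A reader might infer that trivial differences will be reported as real differences between drugs. The protocol supports only the weaker statement that they will be statistically significant, and that significance will not identify which of them matter. The propensity score covariates are described as demographic and clinically relevant variables, not as variables picked by p-value, so the primary rate ratios are not affected.

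**What to change.** In section 9.7.2:
1. Make standardized differences (for means and for proportions) the basis for comparing characteristics between OAC groups, reported for the total sample and for each matched sample.
2. State beforehand the threshold for a relevant difference. The conventional 0.1 is one option; it does not come from the protocol and would need to be adopted explicitly.
3. Use the generalized linear model to give age- and gender-adjusted differences with 95% confidence intervals.
4. Drop the t-tests and chi-square tests, or label any remaining p-values as descriptive.

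The cost is a reworded sentence and one more column in the characteristics tables, built from summaries already planned. No new data are needed. The only loss is less emphasis on p-values.
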